### 3) Age and Reproductive Status

- a) Men and Women, age  $\geq 18$  or age of majority
- b) Women of childbearing potential (WOCBP) must have a negative serum or urine pregnancy test (minimum sensitivity 25 IU/L or equivalent units of HCG) within 24 hours prior to the start of study drug.
- c) Women must not be breastfeeding
- d) WOCBP must agree to follow instructions for method(s) of contraception for the duration of treatment with study drug(s) (abatacept) plus 5 half-lives of study drug (70 days) plus 30 days (duration of ovulatory cycle) for a total of 100 days post-treatment completion
- e) Men who are sexually active with WOCBP must agree to follow instructions for method(s) of contraception for the duration of treatment with study drug(s) (abatacept) plus 5 half-lives of the study drug (70 days) plus 90 days (duration of sperm turnover) for a total of 160 days post-treatment completion. In addition, male subjects must be willing to refrain from sperm donation during this time.
- f) Azoospermic males are exempt from contraceptive requirements. WOCBP who are continuously not heterosexually active are also exempt from contraceptive requirements, and still must undergo pregnancy testing as described in this section.

Investigators shall counsel WOCBP, and male subjects who are sexually active with WOCBP, on the importance of pregnancy prevention and the implications of an unexpected pregnancy. Investigators shall advise on the use of highly effective methods of contraception ([Appendix 1](#)), which have a failure rate of  $< 1\%$  when used consistently and correctly. It is expected that investigators will refer to the Product Insert, as well as local regulations and guidelines for prevention of pregnancy appropriate for the standard background treatment being used by individual subjects.

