### **6.1.1 Serious Adverse Event Collection and Reporting**

Section 5.5.1 in the Investigator Brochure (IB) represent the Reference Safety Information to determine expectedness of serious adverse events for expedited reporting. Following the subject's written consent to participate in the study, all SAEs, whether related or not related to study drug, must be collected, including those thought to be associated with protocol-specified procedures. All SAEs must be collected that occur during the screening period through 24 weeks after discontinuation of dosing.

The investigator must report any SAE that occurs after these time periods and that is believed to be related to study drug or protocol-specified procedure.

An SAE report must be completed for any event where doubt exists regarding its seriousness.

If the investigator believes that an SAE is not related to study drug, but is potentially related to the conditions of the study (such as withdrawal of previous therapy or a complication of a study procedure), the relationship must be specified in the narrative section of the SAE Report Form.

SAEs, whether related or not related to study treatment, and Pregnancies must be reported to BMS (or designee) immediately within 24 hours of awareness of the event.

SAEs must be recorded on the SAE Report Form. The required method for SAE data reporting is through the eCRF. The paper SAE Report Form is only intended as a back-up option when the electronic data capture (EDC) system is unavailable /not functioning for transmission of the eCRF to BMS (or designee). In this case, the paper form is transmitted via email or confirmed facsimile (fax) transmission. When paper forms are used, the original paper forms are to remain on site.

Pregnancies must be recorded on a paper Pregnancy Surveillance Form and transmitted via email or confirmed facsimile (fax) transmission.

[REDACTED]

If only limited information is initially available, follow-up reports are required. (Note: Follow-up SAE reports must include the same investigator term(s) initially reported.)

If an ongoing SAE changes in its intensity or relationship to study drug or if new information becomes available, the SAE report must be updated and submitted within 24 hours to Sponsor or designee using the same procedure used for transmitting the initial SAE report.

All SAEs must be followed to resolution or stabilization.

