6 STUDY PERIODS, TREATMENT REGIMENS AND POPULATIONS FOR ANALYSES

6.1 Study Periods

There are 6 analysis periods defined for the study: the 5 study periods ((i) pre-treatment period; (ii) 24-week DB period; (iii) the OL period; (iv) the OLE period for Japan; (v) the LTE period, incorporating the OLE period for Japan) and (vi) the cumulative abatacept period. These periods will be used in the safety summaries.

The pre-treatment period: covers the time period prior to the first dose date/time of study medication.

The 24-week Double-Blind period: starts at the first dose date/time of double-blind study medication and lasts until the last dose date of the double-blind period + 56 days if subjects discontinue the study during double-blind period, or until the first dose in the open-label period.

Since the dosing information for the Open-Label period, the Open-Label Extension period and the Long-Term Extension period is recorded on the same CRF page, it is not possible to derive the first/last dose for the different periods based on that CRF page. This is why start and end visit dates from other CRF pages will be used to distinguish between these 3 periods. Start and end visit dates are recorded for most periods, except the start of the OLE period for Japan subjects, this will be

assumed to be the end of the OL period. These dates will be used for deciding which dose belongs to which period.

The Open-Label period: starts at the first dose of the open-label period and lasts until the last dose date of open-label period + 56 if subjects discontinue the study during open-label period (or if subjects are from U.S. and Czech Republic sites), or until the first dose in the open-label extension period for subjects from Japanese sites, or the first dose in the long-term extension period for subjects from other sites.

The Open-Label Extension period (Japan subjects only): starts at the first dose of the open-label extension period (determined as the open-label period end visit date from the CRF) and lasts until the last dose date of open-label extension period + 56 if subjects discontinue the study during open-label extension period, or until the first dose in the long-term extension period.

The Long-Term Extension period (all subjects except for U.S. or Czech subjects): starts at the first dose of the long-term extension period and last until the last dose date of long-term extension period + 56.

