7.4.1.1 Exposure during Double-Blind Period

Extent of exposure to double-blind study drug will be summarized using the as-treated analysis population in two ways:

- Number of injections.
- Number of days a subject is known to be on study drug.

The number of injections subjects received will be based on the study medication page of the CRF when an injection date is present.

The number of days the subject is known to be on study drug (exposure to study drug) during 24-week double-blind period is calculated as:

- For subjects who discontinued during 24-week double-blind period or did not enter the open-label period within 56 days of the last injection in the double-blind period:
- Exposure in days = (date of last injection in the 24-week double-blind period - date of first injection for double-blind period + 1) + 56.

For subjects who enter open-label period within 56 days of the last injection of 24-week double-blind period:

- Exposure in days = (date of first injection in the open-label period - date of first injection in the double-blind period).

The offset of 56 days is the length of 2 regular dosing cycles and represents approximately 4 times the half-life of abatacept in humans.

Summaries of exposure to study drug will show the distribution of the number of injections and days on drug, together with the means, standard deviations, medians, minima and maxima, by treatment group.

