Any AEs that occur before the first injection of double-blind study drug or more than 56 days after the last injection during the double-blind period will be excluded from safety summaries in the Week 24 analysis. However, all reported AEs, including AEs that occurred more than 56 days post last dose for subjects who discontinued the study during the double-blind period or completed the double-blind period but chose not to enter the open-label period will appear in the above mentioned comprehensive listing.

Summary information (the number and percent of subjects) regarding AEs (for serious and non-serious events) will be tabulated by SOC, PT and treatment group for:

- Serious adverse events (SAE).
- SAEs related to study drug.
- AEs leading to study drug discontinuation.
- AEs related to study drug.
- AEs related to study medication categorized by intensity.
- Most common related AEs (reported in at least 2% of subjects in any treatment group).
- AEs by intensity.
- All AEs (serious or non-serious).
- Most common (serious or non-serious) AEs (reported in at least 5% of subjects in any treatment group).
- Laboratory AEs are laboratory results identified by the Investigator as AEs and thus reported on the AE pages of the CRF. Any such AE will be included in the respective AE summaries.

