7.6.2.2 Malignancy

All events in the MedDRA Maintenance and Support Services Organization (MSSO) malignancies Structured MedDRA Query (SMQ) list occurring during the double-blind period will be captured and reported. These events will be summarized by preferred term and treatment group and will also be listed.

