Exposure adjusted (per 100 person-years) incidence rates of adverse events accounting for multiple occurrence of an event will be calculated for all AEs/SAEs which occurred during the open-label / open-label extension / long-term extension periods in abatacept treated subjects. The numerator is the number of unique events within the open-label / open-label extension / long-term extension periods (up to 56 days post last abatacept dose during the open-label / open-label extension / long-term extension periods). The denominator is the overall total exposure (person-years) within each period, which is calculated as the sum over all subjects of exposure (in days) divided by 365.25. The resulting incidence rate is multiplied by 100 to express the rate per 100 person-years.

As an example, if 10 patients report 7 unique episodes of headache and had a combined cumulative exposure of 20 years to study medication, the incidence rate is reported as $7 / 20 * (100)$ or 35 cases per 100 patient years of exposure.

For all SAEs, exposure adjusted per 100 person-years rates will be summarized by time-intervals in months: 0-3 months, 3-6 months, 7-9 months, 10-12 months and > 12 months (time-intervals defined as Days 1-90, Days 91-180, Days 181-270, 271-360 and > 360 Days), respectively. In addition, the number of subjects who experienced a SAE, once or multiple times within this period will be presented. The above analyses will be performed for infection and local injection site reaction, respectively. A subject listing of unique AEs will also be provided.

Unique AEs and exposure adjusted multiple events summaries will also be provided separately for the cumulative period. The exposure adjusted per 100 person-years rates will be provided for SAEs, Infections, local injection site reaction. and will be summarized by 3 month time interval for the cumulative period: 0-3 months, 3-6 months, 7-9 months, 10-12 months and > 12 months (time-intervals defined as Days 1-90, Days 91-180, Days 181-270, 271-360 and > 360 Days), respectively.

[REDACTED]

[REDACTED]

- █ [REDACTED]
- █ [REDACTED]
- █ [REDACTED]
- █ [REDACTED]
- █ [REDACTED]

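### For subjects followed off drug, serious events with onset 57 to 168 days after the last dose are collected but enter no visible safety summary, because every summary period ends at 56 days

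*SAP*

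**What the plan says.** **Collection.** Protocol 6.1.1: "All SAEs must be collected that occur during the screening period through 24 weeks after discontinuation of dosing". Protocol 6.1 has every cancer handled as an SAE, so malignancies fall under the same rule. Protocol 3.5 and Table 5.1-7 schedule safety visits 85 and 169 days after the last dose. Under protocol 3.1.2 to 3.1.4 and 3.1.6, these visits are not required of subjects who start abatacept from another source.

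**Summaries.** SAP 7.6.1 keeps out of the Week 24 tables any event with onset "more than 56 days after the last injection during the double-blind period will be excluded from safety summaries in the Week 24 analysis". SAP 6.1 defines the double-blind period so that it "lasts until the last dose date of the double-blind period + 56 days if subjects discontinue the study during double-blind period", and otherwise runs to the first open-label dose. The open-label, Japan extension, long-term and cumulative abatacept periods carry the same 56 days. The exposure-adjusted rates in SAP 11.7 count events "up to 56 days post last abatacept dose during the open-label / open-label extension / long-term extension periods". Protocol 8.4, 8.4.3, 8.4.7 and 8.4.9 use the same limit. The malignancy summary in SAP 7.6.2.2 covers events "occurring during the double-blind period will be captured and reported".

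**Listings.** After the exclusion, SAP 7.6.1 sends to the comprehensive listing "all reported AEs, including AEs that occurred more than 56 days post last dose for subjects who discontinued the study during the double-blind period", and also those of subjects who completed that period but did not go on. The text just before it lists all fatal events, with no day limit.

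**Reason given.** SAP 7.4.1.1: "The offset of 56 days is the length of 2 regular dosing cycles and represents approximately 4 times the half-life of abatacept in humans". Section 11.5.1.1 repeats this.

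**The concern.** The protocol asks sites and subjects for 24 weeks of post-dose safety data, and the analysis plan tabulates the first 8 weeks. Serious infections and malignancies are named safety endpoints in both documents, and SAP 7.6.2 promises risk differences with 95% confidence intervals for the events of interest. A malignancy diagnosed three months after the last dose would be in the database but in neither the numerator nor the person-time of any visible summary. A reader of the report could not compare late events between arms without counting them by hand from a listing.

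The timing of the analyses makes the gap harder to explain. The protocol synopsis and section 8.4 tie the Week 52 analysis to completed follow-up visits as well as to treatment, and SAP section 7 does the same for the final analysis. (The SAP's own statement for Week 52 mentions treatment only.) Analyses timed to take in the follow-up data would then leave most of it untabulated.

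**Working it through.** **Inputs.** Summary cut-off 56 days (SAP 6.1, 7.6.1, 11.7). SAE collection 24 weeks = 24 × 7 = 168 days (protocol 6.1.1). Five half-lives = 70 days (protocol 3.3.1, also 3.1.3). Dosing every 7 days (protocol 4.5.1).

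**1. The plan's own figure.** Half-life = 70 / 5 = 14 days, and 56 / 14 = 4. The four-half-life reason reproduces; the fraction of drug left is 0.5^4 = 6.25%. The dosing-cycle reason does not: two weekly cycles are 2 × 7 = 14 days, and 56 / 7 = 8 doses. Two cycles would make 56 days only if a cycle were 28 days.

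**2. The gap.** 168 − 56 = 112 days, and 112 / 168 = 66.7% of the post-dose collection window. A 70-day cut-off would still leave 168 − 70 = 98 days (58.3%), so it would recover only 14 of the 112. The gap that matters is 56 against 168, not 56 against 70.

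**3. Share of all collected time, per subject with full off-drug follow-up.**
- Stops at Week 12: 112 / (84 + 168) = 112 / 252 = 44%.
- Last dose in Week 51 (Day 51 × 7 + 1 = 358), then no abatacept: 112 / (358 + 168) = 112 / 526 = 21%.
- Completes the long-term extension (last dose Day 1086 of that period), then no abatacept: 112 / (1086 + 168) = 112 / 1254 = 9% of extension plus follow-up.

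**4. Total for the double-blind period.** The documents do not give the number who stop. Assuming 7 to 30 of 150 stop and are all followed to Day 168, the time outside the tables is 7 × 112 / 365.25 = 2.1 to 30 × 112 / 365.25 = 9.2 person-years. Planned double-blind time is 150 × 168 / 365.25 = 69.0 person-years.

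**5. Does another summary pick these events up?**

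| Summary | Who is in it | Where it ends |
|---|---|---|
| Week 24 tables and risk differences | As-treated | Last double-blind dose + 56 days, or first open-label dose |
| SAP 7.8, events up to the Week 24 lock | As-treated, cumulative abatacept period | Last abatacept dose + 56 days |
| Week 52 | Dosed open-label | Last open-label dose + 56 days, or first dose of next period |
| Week 76, Japan | Dosed in the Japan extension | Last extension dose + 56 days, or first long-term dose |
| Final | Dosed in the long-term extension | Last dose + 56 days |
| Cumulative abatacept | Ever dosed with abatacept | Last abatacept dose + 56 days |

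Take a subject who stops at Week 12 and has a malignancy 100 days after the last dose. On placebo, the subject has no cumulative abatacept period and is in no later population. On abatacept, the subject is in the cumulative summaries, but the event falls after they close. A U.S. or Czech subject who completes Week 52 and takes no other abatacept has an open-label period that closes at 56 days, with no extension to follow.

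**6. One text points the other way.** Appendix 3 says each later analysis will assess all the safety data held at its lock. It does not say how this fits the period definitions, and SAP 11.7 then applies the Week 24 analyses to events during those periods.

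**The case against.** The strongest reply is that the 56-day window is deliberate, prespecified and the same in protocol and SAP, and that nothing is hidden. That largely stands. The window is four half-lives on the protocol's own figure. Late double-blind events appear in a listing that shows treatment group. Off-drug events are also harder to attribute, since subjects may by then be on other treatment, and their number may be small.

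Several stronger readings are tempting, and the documents do not support them.
- A reader might infer that late events are never reported. They are listed; what is missing is counts, denominators and rates.
- A reader might infer that the safety comparison rests on one third of follow-up. One third is the share of post-dose time only. All on-treatment time is summarised, and subjects who continue have later events counted in the next period.
- A reader might infer that everything found at the Day 85 and Day 169 visits is dropped. The rule goes by onset: an event that began on Day 30 and was recorded on Day 85 is included.
- A reader might infer that the 70-day figure proves 56 days wrong. It is used for contraception and for starting another biologic, not for assigning events to periods.

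The reply does not meet the remaining point: a listing is not a comparison between arms, and no visible summary replaces it.

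**Conclusion.** The concern holds for subjects who stop study drug and are followed off drug. For them, SAEs, malignancies, serious infections and deaths with onset on Days 57 to 168 have no stated place in any visible count, risk difference or rate. The size is 112 of 168 post-dose days (67%) for a subject with full follow-up. Across the double-blind period this is roughly 2 to 9 person-years beside 69, if 7 to 30 subjects stop. It is smaller to the extent that subjects start abatacept elsewhere and skip the visits. The on-treatment analysis is not wrong; it needs a companion. Two smaller defects go with it: Appendix 3 is ambiguous against the 56-day definitions, and the dosing-cycle reason does not fit weekly dosing. Text before SAP 7.6.1 and after 11.7 is blacked out, so a summary described there could not be checked.

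**What to change.** 1. Keep the 56-day summaries as the on-treatment analysis. Add one supplementary table of deaths, SAEs, malignancies and serious infections with onset through 168 days after the last dose, ending at the first open-label or non-study abatacept dose, with matching person-time. Present it by double-blind group, and by last treatment for the later periods. Flag events after the start of another biologic, and label the table as including off-treatment follow-up.
2. At Week 24, use the follow-up available at the lock and say that it is incomplete. Complete the table at the Week 52 and final analyses, including subjects who stopped in the double-blind period.
3. State in Appendix 3 whether assessing all safety data means beyond 56 days, and align it with SAP 6.1 and protocol 8.4.7 and 8.4.9.
4. In SAP 7.4.1.1 and 11.5.1.1, replace the dosing-cycle reason: 56 days is eight weekly doses. The half-life reason can stay.

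The cost is a few tables from data the protocol already collects. The downsides are confounding by later treatment, which the flag and label make visible, and partial follow-up at the Week 24 lock.

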7.6.2 Adverse Events of Interest

For all adverse events of special interest, treatment groups will be compared descriptively using risk differences and corresponding 95% CI and presented graphically using a forest plot in decreasing order of risk difference.

7.6.2.1 Infections

All reported infections and infestations within the SOC: Infections and infestations occurring during the double-blind period are included in the summaries described in [Section 7.6.1](#).

7.6.2.2 Malignancy

All events in the MedDRA Maintenance and Support Services Organization (MSSO) malignancies Structured MedDRA Query (SMQ) list occurring during the double-blind period will be captured and reported. These events will be summarized by preferred term and treatment group and will also be listed.

7.6.2.3 Autoimmune Disorders

The frequency of pre-specified autoimmune disorders, defined using a BMS custom Autoimmune Disorder SMQ, occurring during the double-blind period will be provided. Autoimmune disorders occurring during the double-blind will also be summarized by intensity. All reported autoimmune disorders occurring during the double-blind period will be listed.

7.6.2.4 Injection Adverse Events

A. Systemic Injection Reactions are defined pre-specified AEs (such as hypersensitivity reactions) occurring during the first 24 hours after SC injection. The pre-specified list of AEs is defined using a BMS custom SMQ for abatacept SC program.

B. Injection Site Reaction Adverse Events: Summaries of injection site reactions will be done in two ways: using the pre-specified list of injection site reactions (cSMQ) and using the standard HLT lists for Injection site reactions, Administration site reactions NEC, and Application and instillation site reactions.

The number and percent of subjects experiencing the injection reactions defined in A and B above will be summarized by SOC and PT and treatment group. The distribution of the injection reaction events of interest by severity will also be provided. Serious events of interest during the double-blind period will be summarized by SOC, PT and treatment group. Most frequent (reported in 5% of subjects or more in any treatment group) AEs will also be provided. All reported injection reactions events of interest occurring during the double-blind period will be listed.

In addition, a pre-specified local injection site reaction event of interest, defined as the AEs with the following PT that occur at the site of SC injection: *Erythema, Pain, Pruritus, Haematoma, and Swelling* will be summarized by severity.

